4. STATISTICAL CONSIDERATIONS/DATA ANALYSIS

4.1. Sample Size

In order to test the effectiveness of the x-IHPC intervention, outcomes from participants in this pilot study will be compared with outcomes from a comparison group of similar families who receive standard nutrition counseling during their regularly scheduled check-ups at HWNV. The team will enroll 25 children in the x-IHPC intervention and the same number in the comparison group (n=50). Both groups of children and guardians will receive standard in-office counseling, but the intervention group will receive the x-IHPC.

4.2. Method of Data Analysis

Analyses will follow the intention-to-treat principle, which categorizes participants by their treatment assignments regardless of adherence to the intervention or incomplete follow-up, and includes them in all analyses. Descriptive statistics will be calculated and reported as mean, standard deviation and 95% confidence intervals for continuous variables and frequency and percentage for categorical variables. Characteristics of study participants will be compared at baseline between the intervention and control groups and tested for significance using the two-sample t-test for continuous variables and the Chi-square test for categorical variables. Comparisons that are significant at the $P<0.10$ level will be considered for inclusion in multivariable models for primary and secondary analyses given that participants will not be randomized to their respective treatment groups.

Primary analyses will examine diet quality, screen time, physical activity, and guardian self-efficacy and confidence of those in the intervention and control groups while controlling for the correlated nature of the repeated measures within participants (i.e. baseline, post-intervention, and 6-month post-intervention). Secondary analyses will compare the BMI of guardians and BMI percentile of children at the three time points between the intervention and control groups. A longitudinal data analysis strategy will be employed with generalized estimating equations with robust CIs for both primary and secondary outcomes (Albert, 1999; Ma et al., 2012). A 2-sided p-value <0.05 will be accepted to indicate statistical significance. Additional analyses will be conducted to determine if results were influenced by other covariates including demographics (age, gender, educational attainment of guardian, income, etc.). All analyses will be conducted in SAS version 9.2.

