Study Design: In order to test the effectiveness of the x-IHPC intervention, outcomes from participants in this pilot study will be compared with outcomes from a comparison group of similar participants who receive standard nutrition counseling during their regularly scheduled check-ups. The team will enroll 25 children in the x-IHPC intervention and the same number in the comparison group (n=50). Both groups will receive standard in-office counseling, but the intervention group will also receive the x-IHPC.

Study Methodology: The comparison group receives standard, in-office counseling at visits 1, 3-months and 6-months. The intervention group receives standard in-office counseling at the same intervals, and also participates in a 12-week x-IHPC developed by a dietitian curriculum specialist. In addition, a key pillar of this study is identifying and training Community Health Workers (CHWs) to be Spanish-speaking facilitators of the x-IHPC and utilizing community engagement strategies. Training these CHWs and including them in designing the x-IHPC curriculum, will ensure that the programming is culturally appropriate; includes local features that relate directly to the community's needs; and enables study facilitators to respond effectively to the questions and learning needs of the parents and children involved in the program.

Statistical Methodology:

To examine the research question, a longitudinal analysis using generalized estimating equations (GEE) will be conducted to assess if mean differences exist on dietary measures, screen time, physical activity and guardian self-efficacy and confidence between the intervention and comparison groups while accounting for the correlation among the repeated measurements and controlling for covariates.

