1.2. Hypothesis

Research Question: Among guardians of children ages 6-12 years who are obese or overweight, does a family-based, culturally-tailored, virtual intervention change knowledge, self-efficacy, and behaviors about modifiable lifestyle practices to promote healthy eating when compared to standard in-office counseling?

Ho: A family-based, culturally-tailored, virtual intervention does not significantly change knowledge, self-efficacy, and behaviors about modifiable lifestyle practices when compared to standard in-office counseling.

Ha: A family-based, culturally-tailored, virtual intervention does significantly change knowledge, self-efficacy, and behaviors about modifiable lifestyle practices when compared to standard in-office counseling.

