2.6. Recruitment

The study employs convenience sampling. Recruitment will take place through email to families who receive care at HWNV in English and Spanish as well as posters advertising the program placed in community spaces where children and families who are clients at HWNV spend time (updated recruitment flyer, Appendix B). If guardians are interested in being part of the program, there will be a contact person listed on the advertisement who will screen for eligibility. If a family is screened as eligible to be part of the x-IHPC intervention, a member of the study team will meet with the family virtually or in person and consent the guardian to be part of the study. This consent process will take place with a trained interpreter. The consent will be emailed to program participants prior to the consent conversation when possible. Whether consent occurs virtually or in person, a hard copy of the consent will be printed and stored by the Inova PI. A copy of the consent will be given to the guardian.

Participants will also be screened for eligibility during their well-child clinic visit at HWNV by the physician study PI. If guardian meets the study inclusion criteria, the PI will introduce the study to the guardian and ask if they would like more information.

Families will decide if they have the capacity to participate in the x-HPC intervention. They will be offered both groups, but can choose which group works for their family. We realize that this introduces selection bias into the study (families who self select to be part of the intervention are families who are interested in health and have the time and ability to attend). However, the intervention takes a lot of time and families need to choose the arm that works for their schedule.

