The x-IHPC will include 4 extra modules, (= 4 additional weeks of programming) that will be developed by a dietitian curriculum specialist. The expanded IHPC will also include programming just for parents to increase their involvement. A key pillar of this study is identifying and training CHWs from HWNV to be Spanish-language facilitators of x-IHPC. Training these CHWs and including them in designing the x-IHPC curriculum will ensure that the programming is culturally appropriate; includes local features that relate directly to the community's needs; and enables facilitators to respond effectively to the questions and learning needs of the parents and children involved in the program.

IHPC provides produce boxes, nutrition and meal-preparation, education, and supportive counseling to address barriers related to obtaining produce and food. The intervention provides participants with a bi-weekly produce box for 12 weeks (6 boxes total) and helps families identify sustainable ways to obtain vegetables once the produce boxes end. Providing produce boxes exposes families to new, unfamiliar vegetables that are not common in their home countries, and allows families to experiment with new recipes on a limited income. The CHW will support families by coaching them on how to prepare these unfamiliar vegetables, give tips on finding sales at grocery stores, as well as by navigation to food assistance sites including food pantries, school meal sites and bus routes, and neighborhood food distributions. Parents will learn strategies to increase vegetable consumption by addressing perceived

barriers – such as the child doesn't like vegetables. Curriculum will also include topics such as how to increase physical activity and reduce screen time. Both the families in the x-HPC and families who receive the in-office counseling will be offered the 6 vegetable food boxes, delivered on a bi-weekly basis during their time in the study.

Families will decide if they have the capacity to participate in the x-HPC intervention. They will be offered both groups, but can choose which group works for their family. We realize that this introduces selection bias into the study (families who self select to be part of the intervention are families who are interested in health and have the time and ability to attend). However, the intervention takes a lot of time and families need to choose the arm that works for their schedule.

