3.5. Consent/Accent

Once a guardian has been screened as eligible for inclusion in the study, they will be approached by the physician PI and asked if they are interested in being part of the study. If they are interested, the PI will discuss whether they are interested in joining the comparison group or the intervention group. A member of the study team will meet with the family virtually or in person and consent the guardian to be part of the study (Appendix D: Consent). This consent process will take place with a trained interpreter. The consent will be provided in both English and Spanish. The consent will be emailed to program participants prior to the

¹⁵ Bryant, M. J., Ward, D. S., Hales, D., Vaughn, A., Tabak, R. G., & Stevens, J. (2008). Reliability and validity of the Healthy Home Survey: a tool to measure factors within homes hypothesized to relate to overweight in children. *The international journal of behavioral nutrition and physical activity*, 5, 23. <https://doi.org/10.1186/1479-5868-5-23>

¹⁶ Schrempf, S., van Jaarsveld, C. H., Fisher, A., & Wardle, J. (2015). The Obesogenic Quality of the Home Environment: Associations with Diet, Physical Activity, TV Viewing, and BMI in Preschool Children. *PloS one*, 10(8), e0134490. <https://doi.org/10.1371/journal.pone.0134490>

¹⁷ Kininmonth, A. R., Schrempf, S., Smith, A., Dye, L., Lawton, C., Fisher, A., Llewellyn, C., & Fildes, A. (2021). The Home Environment Interview and associations with energy balance behaviours and body weight in school-aged children - a feasibility, reliability, and validity study. *The international journal of behavioral nutrition and physical activity*, 18(1), 167. <https://doi.org/10.1186/s12966-021-01235-3>

consent conversation when possible. Whether consent occurs virtually or in person, a hard copy of the consent will be printed and stored by the Inova PI. A copy of the consent will be given to the guardian.

3.6. Monitoring Subjects and Criteria for Withdrawal of Subjects from the Study.

Study participants may leave the study at any time, without penalty. In some cases, the participant may be withdrawn if the HWNV physician PI determines that the study intervention is too burdensome for the participant or is adversely affecting the study participant's health. If any study participant leaves the study or is withdrawn from the study, their data will not be used in analysis.

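### Families choose their arm, but 4.2 selects primary-model covariates by baseline tests at P<0.10, a screen that at 25 per arm often leaves out moderate confounders

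*Combined protocol and SAP*

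**What the plan says.** There is no randomization (section 3.3). Section 3.5 says that "the PI will discuss whether they are interested in joining the comparison group or the intervention group", and section 3.1 explains that "families need to choose the arm that works for their schedule". Section 2.6 names the selection bias and describes those who opt in as "families who are interested in health and have the time and ability to attend".

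Section 4.2 is where the analysis responds. Baseline characteristics are "tested for significance using the two-sample t-test for continuous variables and the Chi-square test for categorical variables", and those with P<0.10 "will be considered for inclusion in multivariable models for primary and secondary analyses given that participants will not be randomized". Nothing says how a flagged variable passes from being considered to being included. Guardian education and income are named in 4.2, but only for additional analyses of covariate influence, in an open-ended list. The abstract promises a GEE "while accounting for the correlation among the repeated measurements and controlling for covariates", without naming the covariates.

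The tested quantity is also left open. The alternative hypothesis in 1.2 is that the program "does significantly change knowledge, self-efficacy, and behaviors about modifiable lifestyle practices when compared to standard in-office counseling", which points to change. Section 4.2 speaks of "controlling for the correlated nature of the repeated measures within participants (i.e. baseline, post-intervention, and 6-month post-intervention" but gives no group-by-time term, baseline handling or primary wave. Section 3.4 collects the survey twice, at the start and the end; 4.2 analyses three time points.

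**The concern.** Confounding by arm choice is the main threat to this comparison. How much a baseline difference biases the result depends on its size and its link to the outcome, not on its P value in 50 families. A significance screen in a sample this small will often pass over differences large enough to matter, and the undefined second step leaves the final model to be chosen after the data are seen.

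The contrast matters too. If the primary quantity is difference in change, a baseline covariate entered only as a main effect may do nothing to it, so a covariate could be adjusted for in name only. The main harm is residual bias in the estimated program effect; the effect on the false-positive rate is smaller.

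**Working it through.** **Inputs from the documents:** 25 per arm, screening threshold P<0.10, t-test and chi-square test, outcome tests two-sided at 0.05, GEE with robust CIs (sections 4.1 and 4.2). Section 4.1 gives no effect size, SD or power, so there is no power figure to reproduce.

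**Assumed, because the documents give none:** covariate imbalance (in covariate SDs), coefficient on change (outcome SD per covariate SD), within-person correlation r of 0.4 to 0.7.

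**1. What the screen detects.** An observed difference must reach t(0.95, 48 df) × √(2/25) = 1.677 × 0.283 ≈ 0.47 SD. For a true imbalance d, the flag rate comes from the noncentral t with noncentrality d × √(25/2):
- d = 0.3 (noncentrality 1.06): 28%
- d = 0.5 (noncentrality 1.77): 54%
- a 40% v 60% split on a yes/no covariate, by exact enumeration: 45% (34% with continuity correction)

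With two independent confounders, at least one is missed in 1 − 0.278² = 92% of trials at 0.3 SD, and in 1 − 0.539² = 71% at 0.5 SD.

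**2. Bias left in the change contrast.** Unadjusted bias is number × imbalance × coefficient; for four confounders at 0.3 and 0.3 it is 4 × 0.3 × 0.3 = 0.36 SD. Simulation with no true effect (change-score regression, selected covariates entered with time terms, r 0.5 to 0.7):

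| Confounders, same direction | Unadjusted | Screened | All included |
|---|---|---|---|
| One | 0.09 | 0.04 | 0.00 |
| Two | 0.18 | 0.07 | 0.00 |
| Four | 0.36 | 0.15 | 0.00 |

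If one of the four pushes the other way, screened bias is 0.08 SD; if two do, it is about 0.

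**3. An incomplete fixed list.** A list holding only two of the four leaves 2 × 0.3 × 0.3 = 0.18 SD, with false positives of 8.6 to 11%. The screen leaves 0.15 SD, with 6 to 8%. If the screen may add to the two listed covariates, only the other two depend on it, so the bias is that of two screened confounders: about 0.07 SD.

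**4. Main effects and the change contrast.** Linear GEE, exchangeable, two waves, complete data, one confounder with imbalance 0.5 and coefficient 0.5 (expected bias 0.5 × 0.5 = 0.25):
- no covariate: 0.248
- covariate main effect: 0.248 (largest difference 4e-16)
- covariate-by-time: −0.013

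Three waves give 0.244, 0.244 and −0.001. The invariance on complete data does not depend on the assumed sizes. With 15% of follow-up missing, the main effect moves the bias only from 0.195 to 0.196.

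**5. Change or baseline adjustment.** Each is unbiased in one case and off by (1 − r) × gap in the other. For a gap that would persist without treatment, baseline adjustment is off by (1 − 0.7) × 0.3 = 0.09 to (1 − 0.4) × 0.5 = 0.30 SD. For a transient gap, difference in change is off by the same amount in the opposite direction.

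**6. Error rate of the robust test.** Four covariates with time terms give 4 + 4 + 4 = 12 mean parameters at two visits, or 6 + 4 + 8 = 18 at three, for 50 families. The uncorrected robust z test then rejects about 7 to 8% under the null; a degrees-of-freedom correction with a t reference brings this to 5.6 to 5.8%.

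**The case against.** The strongest objection is that prespecification is not automatically better. That stands: step 3 shows that a list missing half the confounders does slightly worse than the screen on both bias and false positives. A reader might infer that any fixed list beats the screen; the calculation does not support that, and the remedy must let a screen add covariates.

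Second, the plan is not silent. It discloses the selection bias, calls itself a quasi-experimental pilot, and will examine age, gender, education and income in additional analyses. Inclusion criteria 7 and 8 ask every family for internet access and willingness to commit to the 12-week program, which may narrow differences between arms. All true, but none of it puts a covariate into the primary model, and 4.2 still plans tests at 0.05.

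Third, adjusting for availability could be expensive, because schedule partly determines the arm. With one of four covariates imbalanced by 1.0 to 1.5 SD, power for a 0.5 SD effect at r = 0.5 falls from about 42% to 26 to 30%. But the existing screen flags a 1.0 SD gap 97% of the time, so it would largely share this loss.

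Fourth, one could read the plan as testing a group effect pooled over visits including baseline, which would count a stable 0.3 to 0.5 SD gap as an effect in 21 to 63% of null trials. The abstract's wording permits that reading, but 1.2 points to change, so those rates should not be attributed to the plan. Nor do the documents show that education and income will go uncollected: the Appendix C survey is an example that may change, and clinic records might hold them.

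**Conclusion.** The concern holds in a limited form and should be fixed. The only safeguard written for the primary model is a test-based screen that, at 25 per arm, misses a 0.3 SD imbalance about 72% of the time (100 − 28) and a 0.5 SD imbalance about 46% (100 − 54). Under the four-confounder assumption it removes more than half of the bias (0.36 to 0.15 SD) but not the rest.

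The flag rates depend only on the sample size, the threshold and the assumed true imbalance. The bias figures rest on assumed imbalances, coefficients and directions, and could be near zero if confounders offset one another. The main-effect result is algebraic for a linear GEE with complete data, but matters only if the contrast is difference in change. The documents do not support a claim that the result will be invalid, or that a fixed list would remove selection bias: unmeasured drivers of arm choice remain either way. Confidence is medium.

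**What to change.** In section 4.2:

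- **Covariates.** Always include a short prespecified list in the primary and secondary models, whatever the baseline P values: for example guardian education and income, already named there, plus a measure of time available to attend. Report standardised differences. Let any data-driven screen add to the list, never remove from it.
- **Contrast.** Reconcile the survey waves in 3.4 and 4.2 first, then name the primary contrast. If it is difference in change (group-by-time), as 1.2 suggests, enter the listed covariates with covariate-by-time terms. Give a baseline-adjusted model as a sensitivity analysis, and state that the first assumes a stable gap and the second a transient one.
- **Inference.** Use a small-sample correction with a t reference for the robust standard errors.
- **Data source.** Confirm where each listed covariate comes from, or add items before the final survey goes to the IRB. Where possible, record availability and any need-to-change item before arm preference is discussed. Section 3.5 places that discussion before consent and the Appendix C script calls families after it, so later answers may reflect the choice.
- **Conclusions.** Word them as associational and say that unlisted confounders remain.

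The cost is SAP wording, perhaps about three baseline items, and some power. With four covariate-by-time terms and a true 0.5 SD effect, about 41% falls to 35 to 38% at r = 0.5, and about 61% to 54 to 56% at r = 0.7, for imbalances of 0 to 0.3 SD. The loss grows with imbalance, so the list should stay short.

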2.4. Number of Subjects

The team will enroll 25 children in the x-IHPC intervention and the same number in the comparison group (n=50).

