5. HUMAN SUBJECTS PROTECTION (RISKS, BENEFITS, AND ALTERNATIVES)

5.1. Risks

This study poses minimal physical or psychological risk to the study participants. There is a risk that guardians will find the intervention time-consuming. If the burden of the intervention becomes too great, the participant can leave the study with no consequences.

Any adverse events related to the research study will be reported immediately to the IRB. Reportable events include any physical or psychological harm to any human that is related to the study intervention. Protocol deviations will also be reported to the IRB, including anything related to the study participants' safety, rights, or integrity of the study data.

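### The plan contradicts itself on whether leavers' data are analysed, and neither reading protects the x-IHPC comparison if burden-driven dropout is related to outcome

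*Combined protocol and SAP*

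**What the plan says.** **Analysis set.** Section 4.2 adopts the intention-to-treat principle. It classifies participants by treatment group "regardless of adherence to the intervention or incomplete follow-up, and includes them in all analyses". Section 3.6 says the opposite: "If any study participant leaves the study or is withdrawn from the study, their data will not be used in analysis".

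**Method.** Section 4.2 states: "A longitudinal data analysis strategy will be employed with generalized estimating equations with robust CIs for both primary and secondary outcomes". The abstract and section 4.2 both say that the correlation between repeated measurements will be accounted for. Neither names a working correlation, weights, imputation, a missing-data assumption or a sensitivity analysis. The test criterion is: "A 2-sided p-value <0.05 will be accepted to indicate statistical significance".

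**Reasons for leaving.** Section 5.1 says: "There is a risk that guardians will find the intervention time-consuming", and then: "If the burden of the intervention becomes too great, the participant can leave the study with no consequences". Section 3.6 lets the physician investigator withdraw a participant on judging that "the study intervention is too burdensome for the participant". Under sections 2.1 and 3.2 only the intervention group receives x-IHPC.

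**Size and survey times.** There are 25 children per group (section 2.4). Section 3.4 collects the survey at the outset and at the end of the study, whereas section 4.2 analyses three time points.

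**The concern.** The two rules for leavers define different analyses. Under section 4.2, a leaver's baseline survey stays in and the missing follow-up is absent. Under section 3.6, the leaver disappears altogether. A statistician following one section would report a different estimate from one following the other.

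Neither rule deals with dropout related to outcome. Keeping someone in the analysis set does not supply the follow-up survey that they did not give. Unweighted GEE on available visits generally needs missingness that is completely at random or explained by covariates in the model. A completers-only analysis compares a selected x-IHPC group with a comparison group that has no such exit route. Capacity to attend is plausibly linked to guardian confidence and self-efficacy, which are primary outcomes. With 25 families per arm, a few selective exits could move the result.

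**Working it through.** The documents give no effect size, SD, correlation, power or dropout rate, so there is no figure of the plan's own to reproduce. The check asks how far each reading departs from zero when the program has no effect.

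**From the documents:** 25 per arm; two-sided 0.05; GEE with robust confidence intervals; two survey times (section 3.4), so a leaver has a baseline survey only.

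**Assumed:** a continuous, normal outcome with SD 1, higher being better; baseline to follow-up correlation ρ of 0.5 to 0.7; 10% random dropout in the comparison arm, which adds no expected bias; x-IHPC dropout d of 20% to 40%, with log-odds of leaving raised by b = 0.7 to 1.2 per SD of worse baseline.

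**Step 1, who stays.** Let p(y) = 1/(1 + exp(−(a − b·y))) be the chance of leaving at baseline y, with a set so that the average of p is d. The stayers' mean baseline is m = ∫ y(1 − p(y))φ(y)dy / (1 − d). Numerical integration gives m = 0.130 for d = 20%, b = 0.7, and m = 0.375 for d = 40%, b = 1.2.

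**Step 2, bias in the arm-by-time effect.** The stayers' mean follow-up is ρ·m.
- Independence GEE on observed visits keeps the full baseline mean of 0, so its bias is ρ·m.
- Completers-only uses the stayers' baseline mean m, so its bias is ρ·m − m = −(1 − ρ)·m.

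| d | b | m | ρ | Independence GEE | Completers-only |
|---|---|---|---|---|---|
| 20% | 0.7 | 0.130 | 0.5 | +0.065 | −0.065 |
| 20% | 0.7 | 0.130 | 0.7 | +0.091 | −0.039 |
| 40% | 1.2 | 0.375 | 0.5 | +0.188 | −0.188 |
| 40% | 1.2 | 0.375 | 0.7 | +0.263 | −0.113 |

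The gap between the two readings is ρ·m + (1 − ρ)·m = m. The unresolved choice of analysis set alone therefore moves the estimate by 0.13 to 0.38 SD.

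**Step 3, methods that use the baseline.** Given baseline, expected follow-up is ρ·y for stayers and leavers alike, so an estimator that conditions on baseline recovers zero. In simulation, a baseline-regression (maximum likelihood) estimator was biased by at most 0.005 SD. GEE with an estimated exchangeable correlation was biased by about 0.01 to 0.02 SD.

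**Step 4, type I error at 25 per arm (simulation, independence GEE, robust SE).** It was about 7% (d = 30%, ρ = 0.5, b = 0.7), 12% (30%, 0.7, 1.2) and 15% (40%, 0.7, 1.2), against about 6% when dropout was uninformative. Exchangeable GEE gave 6.0% to 7.2%.

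**Step 5, direction.** If families with better baseline values leave, every sign in the table reverses. If dropout in x-IHPC alone is unrelated to outcome, the bias is about zero for every method.

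**Step 6, dropout that follows the unseen follow-up value.** Take ρ = 0.5, dropout in x-IHPC only, and a leaving propensity correlated c = 1/√2 = 0.71 with a worse follow-up value. With λ = φ(z₁₋d)/(1 − d), the bias is c·λ for independence, c·λ(1 − ρ²) for exchangeable and c·λ(1 − ρ) for completers-only. At d = 40%, λ = 0.386/0.6 = 0.644 and c·λ = 0.455.

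| d | Independence | Exchangeable | Completers-only |
|---|---|---|---|
| 10% | +0.14 | +0.10 | +0.07 |
| 20% | +0.25 | +0.19 | +0.12 |
| 40% | +0.46 | +0.34 | +0.23 |

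Here the exchangeable structure no longer removes the bias.

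**The case against.** A reader might infer that the protocol expects burdened families to leave x-IHPC, and that the planned GEE therefore favours the program. The documents do not support that.

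- **They permit such exits but do not forecast them.** Section 5.1 speaks of a risk and section 3.6 of some cases. No rate or imbalance is given. Families choose the arm that suits their schedule (section 2.6), and guardians must be willing to commit to 12 weeks (section 2.7). Both may lower burden-driven dropout.
- **They do not say who leaves.** Busy but better-placed families might go, which reverses the sign.
- **Observed-visit GEE is only one reading.** Section 3.6 removes leavers, and in the same scenarios that pushes the estimate against x-IHPC.
- **GEE does not always need dropout unrelated to outcome.** Missingness explained by modelled covariates is acceptable. For a continuous outcome, a correct exchangeable correlation nearly removes baseline-dependent bias. Since the plan says correlation will be accounted for, exchangeable is at least as natural a reading as independence.

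All of this stands, and it rules out a directional claim. It does not rescue the plan. The working correlation is still unstated, the two sections still conflict, and willingness to commit does not make later exits independent of outcome. Section 2.6 openly accepts selection bias in the choice of arm, but that does not cover selective loss afterwards.

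**Conclusion.** The concern holds in conditional form. Sections 3.6 and 4.2 contradict each other on leavers' data, and neither resulting analysis is reliably valid when dropout depends on outcome.

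If worse-baseline families leave x-IHPC at the assumed rates, independence GEE errs by about +0.07 to +0.26 SD and a completers-only analysis by about −0.04 to −0.19 SD. If better-off families leave, the signs reverse. If dropout is unrelated to outcome, there is no bias. If it depends only on baseline, a correctly specified exchangeable GEE or a likelihood analysis is nearly unbiased.

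The contradiction and the missing specification are facts of the text. The sizes rest entirely on assumed dropout rates, slopes, correlations and a continuous outcome. The plan should be changed because the remedy is cheap, not because a bias toward x-IHPC has been shown.

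**What to change.** 1. Delete the section 3.6 sentence that excludes leavers' data, so that everything already collected is kept, in line with section 4.2. If the consent form makes the same promise, it needs the same change.
2. State the missing-data assumption, and run the primary and secondary comparisons with a method valid when dropout depends on observed data. One option is GEE on data multiply imputed by arm from baseline outcome and demographics. The other is a likelihood-based mixed model with unstructured covariance and small-sample degrees of freedom. If GEE is used, name the working correlation.
3. Add one delta-shift sensitivity analysis for dropouts, because step 6 shows a bias that working correlation cannot remove.
4. Report dropout by arm and reason.
5. Reconcile the two survey times in section 3.4 with the three in section 4.2, since this decides what a leaver can contribute.

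The cost is SAP wording, a little programming and slightly more model dependence. At 40% dropout, 25 × 0.6 = 15 families would inform imputation in x-IHPC, so the list of demographics should be short.
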